Dietary intervention with a high intake of vitamin K of 500mcg for 6 weeks, increases VK and OC serum levels, decreases insulin and leptin levels and reduces cardiovascular risk in young adults, with and without overweight or obesity.

Aims

General aim

To evaluate the effect of dietary intervention with a high intake of vitamin K of 500mcg on serum levels of vitamin K, insulin, osteocalcin, leptin and on cardiovascular risk in young adults with and without overweight or obesity.

Specific aims

- Design a dietary intervention with a 500mcg of vitamin K

- Compare serum levels of vitamin K, insulin, osteocalcin, leptin and cardiovascular risk markers before and after the intervention with high vitamin K intake in subjects with and without overweight or obesity.
- Analyze the relation between vitamin K serum levels and body composition characteristics, metabolic markers and insulin, osteocalcin, leptin and cardiovascular risk percentage in subjects with and without overweight or obesity.

Ethical considerations:

The study will adhere to the regulations established by the Mexican government in the regulations of the general health law regarding health research.

It will be carried out in accordance with the ethical standards and principles for medical research on human subjects established in the Declaration of Helsinki in Helsinki, Finland in 1964, updated in 2008 in Seoul, South Korea.

The subjects who will participate in the study will voluntarily sign the informed consent letter. The project aims to contribute to the study of metabolic diseases in adults and young people with the aim of finding strategies for prevention or use as early dietary treatment and the consideration of foods with a high supply of vitamin K. The participants in the study will be assigned an identification key to guarantee the reliability of their clinical data. If they decide to withdraw from the study, the clinical history and biological samples associated with the individual will be deleted. All individuals who participate in the study will benefit from obtaining and explaining their clinical data, information about the cardiovascular risk they have at the time of the intervention and after it, in addition to being provided with nutritional care and intervention by professionals of nutrition, all this without costs.

Biosafety aspects:

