This is an investigation with minimal risk, the laboratory has the necessary infrastructure and materials for the management of RPBI according to the Official Mexican STANDARD NOM-087-ECOL-SSA1-2002, Environmental protection - Environmental health - Biological hazardous waste - infectious

- Classification and handling specifications. Waste from the use of reagents for ELISA and wet chemistry will be discarded according to the manufacturer's criteria. The reagents will be stored according to what is stipulated in the manufacturer's sheets and according to the provisions of NOM-054-SEMARNAT1993 and NOM-052-SEMARNAT-2005, no toxic, radioactive or explosive reagents will be worked with. The implementation of the project will be subject to what is described in the General Health Law on health research, DOF reform 04-02-2014 Art. 13 to 17. The main researcher has been trained by the CUCS Biosafety Committee.

METHODOLOGY

Technical methods and instruments for collection, recording, processing and analysis:

- Peripheral blood samples will be taken by venipuncture using the Vacutainer® system.
- The serum variables of glucose, triglycerides and lipids will be obtained by means of colorimetric enzymatic reagents. Vitamin K and insulin will be obtained through ELISA Kits.
- Anthropometric measurements will be carried out using a TANITA brand bioimpedance scale, SECA brand measuring tape and Slim Guide brand plicometers. All measurements will be taken according to ISAK.
- Blood pressure will be measured with an OMRON brand baumanometer.
- Patient data will be recorded in a log and in an Excel database. For the statistical processing of the data, the Excel, SPSS Statistics version 20.0 and GraphPad Prism 8 programs will be used.

Research organization:

The study will be carried out at the University of Guadalajara, Department of Molecular Biology and Genomics, Biochemistry Research Laboratory of the University Center for Health Sciences.

1. Once the patients are included, an initial evaluation will be carried out that consists of:

- Evaluation of nutritional status: Dietary analysis by 24-hour recall, anthropometric analysis (with bioimpedance, measurement of skin folds and circumferences), clinical history.
- Blood sample collection: determination of glucose and serum lipids, vitamin K, insulin and osteocalcin.
- Blood pressure measurement.
- Dietary intervention: Explanation of the study and dietary indications.

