2. Dietary intervention with a high intake of vitamin K for 6 weeks

- Weekly monitoring of dietary adherence
- Nutritional advice: resolve doubts, evaluation of dietary adherence.

3. Final evaluation

- Evaluation of nutritional status: anthropometric analysis.
- Blood sample collection: determination of glucose and serum lipids, vitamin K, insulin, osteocalcin and leptin.
- Blood pressure measurement.
- Final evaluation of dietary adherence through a survey.

4. Data analysis, statistics.

5. Results report

Statistical analysis:

The statistical analysis will be carried out with the statistical package SPSS version 20, GraphPad Prism 9 and Excel 2011. Initially, the Kolmogorov-Smirnov test will be applied to all variables to verify if they followed a normal distribution model. Those variables that followed a normal distribution will be analyzed using parametric tests; Otherwise, non-parametric statistics will be applied.

Descriptive Analysis: mean, standard deviation, standard error of the mean, minimum, maximum and range. Inferential Analysis: Parametric tests (Student's t for independent samples), non-parametric tests (Kruskal Wallis). Comparative analysis: Chi square. Correlations: Spearman for non-parametric and Pearson for parametric tests.

Probability values less than 0.05 will be considered significant.

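### The before-after aim has no paired test: the tests named for continuous outcomes assume independent groups, and leptin has no listed baseline

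*Combined protocol and SAP*

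**What the plan says.** The Work hypothesis is worded as change over the intervention. Among other things it expects that the diet "decreases insulin and leptin levels and reduces cardiovascular risk in young adults". The General aim is "To evaluate the effect of dietary intervention with a high intake of vitamin K of 500mcg on serum levels" of several markers. The second Specific aim is explicit about the contrast: "Compare serum levels of vitamin K, insulin, osteocalcin, leptin and cardiovascular risk markers before and after the intervention", in people with and without excess weight.

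Research organization describes a single sequence for all participants: an initial evaluation, then "Dietary intervention with a high intake of vitamin K for 6 weeks", then a final evaluation. No comparison diet is described.

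Statistical analysis first states that "the Kolmogorov-Smirnov test will be applied to all variables to verify if they followed a normal distribution model", and then: "Those variables that followed a normal distribution will be analyzed using parametric tests; Otherwise, non-parametric statistics will be applied". The tests are then named: "Inferential Analysis: Parametric tests (Student's t for independent samples), non-parametric tests (Kruskal Wallis"). Chi-square is listed as well, with Pearson and Spearman correlations and a 0.05 significance threshold.

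On leptin, the initial blood sample in Research organization covers "determination of glucose and serum lipids, vitamin K, insulin and osteocalcin". The final sample has the same list with leptin added.

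**The concern.** Two measurements on one person are not independent, and the within-person change is the only contrast in this design that can address the General aim. The two tests named for comparing continuous outcomes both require independent groups. The correlations serve the separate aim of relating vitamin K to other characteristics, and chi-square is for categorical data.

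If the named tests are applied to before versus after values, the standard error is wrong; with positive within-person correlation it is too large, and a real change may be missed. If they are meant only for contrasts between weight groups, that loss does not arise, but the study's main question then has no specified test and the choice is left open until the data are in hand.

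The rule for choosing between parametric and non-parametric tests adds a smaller problem. It is written for each variable, whereas a paired t-test depends on the distribution of the within-person differences.

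The leptin gap is a separate matter. A hypothesised decrease cannot be shown without a starting value, and no later analysis can supply one.

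**Working it through.** **Reading the text**

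| Question | Where | Answer |
|---|---|---|
| What is compared? | Specific aims | Before versus after, same people |
| How many diets? | Research organization | One, for everyone |
| Tests for comparing continuous outcomes | Statistical analysis | Independent-samples t; Kruskal-Wallis |
| Paired t, signed-rank, repeated-measures, mixed-model or change-score method | Whole document | None |
| Leptin in hypothesis, General aim, before-after aim | Work hypothesis, Aims | Yes |
| Leptin in initial blood sample | Research organization, item 1 | Not listed |
| Leptin in final blood sample | Research organization, item 3 | Listed |

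**Size of the loss if the listed tests are used on before versus after values**

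The plan has no figure of its own to reproduce: it gives no sample size, SD, effect size or correlation. Assumed inputs: equal variance σ² at both times; within-person correlation r = 0.3, 0.5 or 0.7; two-sided 5% (the plan gives 0.05 but not the sidedness); an effect that a paired test detects with 80% power.

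With n people, the true variance of the mean difference is 2σ²(1 − r)/n. The independent test assumes 2σ²/n. From this:

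- Standard-error ratio = 1/√(1 − r). At r = 0.5 this is 1/0.707 = 1.41.
- Actual type I error = 2[1 − Φ(1.96/√(1 − r))]. At r = 0.5 this is 2[1 − Φ(2.77)] = 0.56%.
- Power = Φ(2.80 − 1.96/√(1 − r)), where 2.80 = 1.96 + 0.84. At r = 0.5 this is Φ(0.03) = 51%.
- Reported p when the correct paired p is 0.01 = 2[1 − Φ(2.576√(1 − r))]. At r = 0.5 this is 2[1 − Φ(1.82)] = 0.07.
- Sample-size multiple to regain 80% power = [(1.96 + 0.84√(1 − r))/(2.80√(1 − r))]². At r = 0.5 this is 1.29² = 1.66.

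| | r = 0.3 | r = 0.5 | r = 0.7 |
|---|---|---|---|
| Standard-error ratio | 1.20 | 1.41 | 1.83 |
| Actual type I error | 1.9% | 0.56% | 0.035% |
| Power (paired = 80%) | 68% | 51% | 22% |
| Reported p (paired p = 0.01) | 0.03 | 0.07 | 0.16 |
| Sample-size multiple | 1.29 | 1.66 | 2.49 |

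Simulation with bivariate normal data, and the effect again set for 80% paired power, gives at r = 0.3 / 0.5 / 0.7:

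- independent t, 20 pairs: 70 / 54 / 26%
- independent t, 30 pairs: 69 / 53 / 25%
- independent t, 50 pairs: 69 / 52 / 24%
- Kruskal-Wallis, 30 pairs: 67 / 50 / 23%, against 78% for the Wilcoxon signed-rank test

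At r = 0 there is no error. At negative r the direction reverses: the type I error at r = −0.3 is 2[1 − Φ(1.96/√1.3)] = 8.6%.

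**The same loss with a fixed effect**

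Holding paired power at 80% makes the assumed effect shrink as r rises. With 30 pairs it is 0.63, 0.53 and 0.41 SD. Holding the shift at 0.5 SD with 30 pairs instead, simulated power at r = 0.3 / 0.5 / 0.7 is 61 / 75 / 93% for the paired t-test, while the independent t stays near 47% throughout. The loss is therefore the gain from pairing that is given up.

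**The case against.** The best defence is that the text shows an omission and not a wrong choice. The general rule speaks of parametric and non-parametric methods and does not exclude paired forms, and nothing says that the independent t-test will be run on before versus after values. There is also a valid use of the listed tests: comparing within-person change between weight groups, which one reading of the aim allows. That use is sound, but it shows whether the groups differ in their change, not whether either group changed, and the plan defines no change score. The gap remains on every reading.

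The magnitudes are hypothetical and apply to one reading only. That is true, and they should be read as a range under stated assumptions. The error is also conservative at any positive correlation.

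The normality point is minor: the phrase about all variables could be taken to include change variables. It matters mainly because adding a paired test requires saying where the check applies.

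The leptin omission may well be a drafting slip. The aim itself requires a starting value, blood is drawn at baseline, and the description of laboratory methods also leaves out osteocalcin, which is in both panels. Even so, the schedule as listed yields no baseline leptin.

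Two further cautions stand. Testing several markers in each weight group at an unadjusted 0.05 multiplies the tests. And without a comparison diet, a paired test shows change, not that the diet caused it. Neither caution removes the need for a paired test.

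**Conclusion.** The concern holds, and it should be fixed before analysis. The plan's main comparison is within person, and the plan names no test for it. Followed literally, it gives that comparison either a test with the wrong standard error or no test at all.

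In the first case, large-sample power falls from 80% to between 68% and 22% over r = 0.3 to 0.7, with no inflation of false positives. This rests on the assumed correlation, equal variances and a two-sided 5% level, none of which the documents supply in full. In the second case there is no power loss, but the central analysis is unspecified.

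The finding that no paired test is named, and that leptin has no listed baseline, rests on the text alone and needs none of these assumptions. As listed, the change in leptin cannot be estimated.

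**What to change.** **Test for change.** Add to Statistical analysis: *Before-after change within each weight group will be tested with a paired t-test, or with a Wilcoxon signed-rank test if the Kolmogorov-Smirnov test on the within-person differences gives p < 0.05.* This keeps the plan's own normality test and threshold, and moves the check to the differences. If the sponsor prefers to test all participants together, the sentence should say so. Keep the independent-samples t-test and Kruskal-Wallis for contrasts between weight groups. If change itself is compared between those groups, apply them to within-person change scores; for the t-test this is equivalent to a group-by-time term.

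The cost is one or two sentences, and the software already named runs these tests. A paired test needs both values for each person and has fewer degrees of freedom (with 30 pairs, critical t is 2.045 instead of 2.002), so it is slightly less efficient only if r is near zero.

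**Leptin.** Reconcile the entries: either list leptin in the initial blood sample under Research organization, or remove it from the hypothesis, the General aim and the before-after aim. The cost is possibly one added baseline assay, or an edit to the hypothesis and aims.

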STUDY PROTOCOL

Overweight and obesity are public health problems worldwide and in Mexico, both related to the increase in weight and body fat that are risk factors for the development of chronic degenerative diseases such as type 2 diabetes mellitus (DM2) and cardiovascular diseases (CVD). The World Health Organization (WHO) defines obesity as the excessive accumulation of fat that can harm health and is diagnosed when the Body Mass Index (BMI) is greater than or equal to 30 kg/m².

In Mexico, according to figures from the National Health and Nutrition Survey (ENSANUT), at the national level, 75.2% of adults are overweight or obese (39.1% overweight and 36.1% obese), with respect to chronic degenerative diseases there is a prevalence of 10.3 % for diabetes, 18.4% for hypertension and it has been reported that 19.5% of the population has elevated cholesterol and triglycerides.

Correct diet and a healthy lifestyle are factors that help to avoid overweight and obesity; However, the current diet of the adult Mexican population is not adequate, because there is low consumption of the recommended food groups. Fruits and vegetables are healthy foods that less than 50% of the country's population consume daily. Regarding other recommended food groups, eggs are consumed by 29.9% of the population, dairy products by 47%. and unprocessed meats by 64.6%. Which is inadequate, due to the vitamins and minerals that these food groups provide.

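### Any t test between the weight groups should default to Welch's unequal-variance form, because nothing in the plan protects the pooled Student's t if the groups differ in both size and spread

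*Combined protocol and SAP*

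**What the plan says.** The Statistical analysis section (under Methodology) names the inferential tests in one line: "Inferential Analysis: Parametric tests (Student's t for independent samples), non-parametric tests (Kruskal Wallis". The choice between the two branches rests on distributional shape: "Initially, the Kolmogorov-Smirnov test will be applied to all variables to verify if they followed a normal distribution model". The threshold is "Probability values less than 0.05 will be considered significant", with sidedness not stated. The section does not mention equality of variances, Welch's correction or a variance test, and it does not assign either test to a particular comparison.

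The groups come from the Work hypothesis and the Aims. The general aim concerns effects on serum markers and "on cardiovascular risk in young adults with and without overweight or obesity". No control arm or allocation step is described, so a participant's group follows from weight status. No sample size, group size, quota or SD is given. The specific aim that is worded as a comparison runs within subjects: "Compare serum levels of vitamin K, insulin, osteocalcin, leptin and cardiovascular risk markers before and after the intervention".

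The only figure that bears on a group ratio is in the introduction, where national survey data are cited: "75.2% of adults are overweight or obese (39.1% overweight and 36.1% obese".

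**The concern.** The pooled t test assumes one common variance. When that assumption fails, equal group sizes largely protect the test and unequal sizes do not. The pooled variance is weighted towards the larger group, so the standard error is too small if the smaller group is the more variable one, and too large if the larger group is.

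This plan has no such protection. Groups formed by weight status, with no balance rule, can easily end up unequal. The group with excess weight combines two BMI classes, so a wider spread in insulin, leptin or body composition is plausible, though the documents do not establish it. A normality check looks at shape and would not detect unequal spread. What is at stake is the p-value and standard error of any between-weight-group t test: false positives in one direction, lost power in the other, depending on which group happens to be larger.

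**Working it through.** The plan states no sample size, power, SD or group size, so there is no figure of its own to reproduce.

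**Inputs**
- From the Statistical analysis section: alpha 0.05, taken as two-sided (assumption).
- Assumed: 60 people in total, normal data, SD 1 in the normal-weight group and SD *r* in the overweight/obesity group, with *r* = 1.5, 2 or 2.5.
- Assumed group sizes, written normal-weight/overweight-obesity: 30/30, 40/20, 45/15 and 15/45. The last is roughly the ratio that would follow if recruitment mirrored the 75.2% prevalence (0.752 × 60 ≈ 45). That is also an assumption.

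**Large-sample formula for the pooled t**

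With n₁ and s₁ = *r* for the overweight/obesity group, and n₂ and s₂ = 1 for the normal-weight group:

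- pooled variance sp² = [(n₁−1)r² + (n₂−1)] / (n₁+n₂−2)
- k² = sp²(1/n₁ + 1/n₂) / (r²/n₁ + 1/n₂)
- true size ≈ 2[1 − Φ(1.96k)]

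**Worked at r = 2**
- 45/15 (more variable group smaller): sp² = (14×4 + 44)/58 = 1.724. Variance used = 1.724 × 0.0889 = 0.153. True variance = 4/15 + 1/45 = 0.289. k² = 0.530, k = 0.728, size = 2[1 − Φ(1.428)] = 15.3%.
- 15/45 (more variable group larger): sp² = (44×4 + 14)/58 = 3.276. Variance used = 3.276 × 0.0889 = 0.291. True variance = 4/45 + 1/15 = 0.156. k² = 1.872, k = 1.368, size = 2[1 − Φ(2.682)] = 0.7%.
- 30/30: sp² = (29×4 + 29)/58 = 2.5. Variance used = true variance = 0.167. k = 1, size = 5%.
- Equal SDs (r = 1): k = 1 at any split, size = 5%.

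**Simulation** (no true difference, 40,000 replicates per cell)

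| Normal-weight / overweight-obesity | Student's t, r = 1.5 to 2.5 |
|---|---|
| 45/15 | 10.5% to 18.4% |
| 40/20 | 8.5% to 12.6% |
| 30/30 | 5.1% to 5.4% |
| 15/45 | 1.7% down to 0.5% |

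Welch's t gives 4.8% to 5.2% in every cell. A separate run with smaller totals shows the same pattern. With the more variable group first and SD ratio 2, Student's t rejects 15.3% at 10/30 and 0.9% at 30/10. A mild imbalance of 25/35 with ratio 1.5 gives 6.6%. Across that run Welch's t stays between 4.7% and 5.3%.

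**Power at 15/45, r = 2, true difference 1.0 normal-group SD**
- True standard error = √0.156 = 0.394, so the standardised difference is 1/0.394 = 2.54.
- Welch's t: Φ(2.54 − 1.96) ≈ 72%; simulated 70%.
- Student's t: Φ(2.54 − 2.68) ≈ 44%; simulated 43%.

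**Cost of Welch's t when variances are equal** (difference 0.8 SD): 73% power against 75% for Student's t at 15/45, and no loss at 30/30.

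**The case against.** The strongest reply is that this is a conditional risk in an inferred contrast. Three parts of it stand.

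- The plan does not assign the t test to the weight-group comparison, and the one aim worded as a comparison is before against after. The link is an inference: an independent-samples test has no other evident use when the only independent groups are the weight groups.
- The plan does not say that variances will be pooled. SPSS, one of the named packages, prints the unequal-variance row as well, so the plan is silent on which row will be reported. The pooled form is the conventional meaning of the name, no more.
- The triggering condition cannot be checked. With equal groups or equal SDs there is almost nothing to correct. If skewed markers such as insulin and leptin were analysed on a log scale, some of the unequal spread might also go.

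A reader might infer more than this, in three ways that the documents do not support.

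- *That false positives will be inflated.* The only figure available, the national prevalence, points the other way: an overweight/obesity majority with the larger spread makes the test conservative. Even that figure describes adults nationally and is not a recruitment plan for young adults.
- *That the Kruskal-Wallis branch is equally faulty.* That test keeps its level under its own null of identical distributions. It departs from 5% only when read as a test of means or medians, and then generally by less than the pooled t.
- *That the plan lacks an overall test for three BMI classes.* The aims read as two groups, and Kruskal-Wallis is valid with two. A three-class analysis is not planned.

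What survives the reply is that nothing in the plan rules out the exposed situation, and removing the exposure costs almost nothing.

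**Conclusion.** The point holds as a cheap improvement, not as a demonstrated error. As written, the plan leaves any t test between the weight groups open to a type I error anywhere from about 0.5% to about 18% at a nominal 5%, with the direction unknown in advance. That range rests on assumed values (60 people, a 3:1 split one way or the other, SD ratio 1.5 to 2.5, normal data), none of which the documents supply. If recruitment did mirror the national prevalence and the heavier group were the more variable, the harm would be lost power, about 27 points (70% − 43%) in the case worked above.

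The missing paired or change-score analysis for the before/after aim is a separate and more basic gap. Resolving it would not remove this exposure, because a comparison of changes between weight groups raises the same variance question.

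**What to change.** In the Statistical analysis section, replace the independent-samples Student's t with Welch's unequal-variance t as the default for any comparison between the weight groups, whether of baseline values or of change. State that no preliminary variance test will be used to choose between the two forms. Settling this before data are seen also removes the option of picking between the two t-test rows afterwards.

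The cost is one sentence of wording, no extra data and no new software. The statistical cost is about 2 points of power when variances are equal and groups are unequal (73% against 75% at 15/45), and none with equal groups. The change does not supply the paired before/after test that the specific aim needs, which must be added separately.

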Vitamins are considered micronutrients and they play an essential role in metabolism. Vitamins are classified according to their nature as fat-soluble or water-soluble. Water-soluble vitamins include vitamin B1, B1, B2, B3, B5, B6, B7, B9, B12 and C, while fat-soluble vitamins are vitamins A, E, D and K. Vitamin K (VK) has two main structural forms, which are phylloquinone (K1) which is found naturally in plant foods, mainly in green leafy vegetables, and menaquinone (K2) which is produced in the intestine and is found in some fermented foods. VK acts as a cofactor for the carboxylation of glutamic acid residues in proteins involved in blood coagulation and bone metabolism, facilitating calcium uptake through the carboxylation of the protein osteocalcin. This last protein, osteocalcin in its carboxylated form (OCc), serves as an indicator of the level of VK, the more OCc exists in the blood it is considered that there is a good level of VK, the osteocalcin that is not carboxylated thanks to the VK, circulates in the blood and is known as undercarboxylated osteocalcin (OCuc). VK requirements are 120mcg/day for men and 90mcg/day for women; Although VK is fat-soluble, the body stores small amounts that are quickly depleted without regular daily ingestion.

Various studies mention that the high intake of VK has positive effects on insulin sensitivity and cardiovascular risk; likewise, VK deficiency is negatively associated with the same factors. Yoshida et al. suggest that the increase of VK intake through diet can reduce the progression of insulin resistance. The mechanism through which VK improves insulin sensitivity is unknown. In animals, OCuc has been shown to stimulate beta cell proliferation and increase insulin secretion; However, Yoshida et al. found that in subjects receiving VK supplements the OCuc levels were lower and the insulin resistance was reduced, compared to the control group without supplements. This suggests

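### If both sexes enrol, the planned unadjusted correlations, and any comparison between weight groups, can reflect sex; the within-person before-after comparison is not affected

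*Combined protocol and SAP*

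**What the plan says.** The Statistical analysis section of the combined protocol and SAP gives the whole inferential plan in a few lines. For group comparisons: "Inferential Analysis: Parametric tests (Student's t for independent samples), non-parametric tests (Kruskal Wallis" test). For categorical data: "Comparative analysis: Chi square", with the variables not named. For associations: "Correlations: Spearman for non-parametric and Pearson for parametric tests". The threshold is given as "Probability values less than 0.05 will be considered significant". No regression, covariate, stratification, matching or partial correlation is named.

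The third specific aim relates serum vitamin K to body composition, metabolic markers, insulin, osteocalcin, leptin and cardiovascular risk. The second specific aim is a before-after comparison in people with and without excess weight. The aims, methodology and analysis sections do not mention sex.

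Sex appears in one place that bears on the exposure. The background states that "VK requirements are 120mcg/day for men and 90mcg/day for women". The intake target is the same for everyone: "Dietary intervention with a high intake of vitamin K of 500mcg for 6 weeks".

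**The concern.** Weight status is a characteristic people bring to the study. Nothing in the design makes the groups alike in sex, and nothing in the analysis corrects for a difference.

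Two kinds of result are exposed, under different conditions.

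- **Correlations (third aim).** If serum vitamin K and a second marker both differ on average between men and women, pooling the sexes produces a correlation even when the two are unrelated within each sex. This needs no imbalance between weight groups.
- **Contrasts between weight groups, of levels or of changes.** These are distorted only if the outcome differs by sex and the share of women also differs between the groups.

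At stake is a sex difference being reported as a link between vitamin K and metabolic or body-composition markers, or as an effect of weight status.

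**Working it through.** **Inputs from the documents.** Requirements of 120 mcg/day (men) and 90 mcg/day (women); intake target 500 mcg; significance threshold 0.05. There is no sample size, SD, effect size or sex mix, so there is no design figure to reproduce.

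**Document arithmetic.** 500/120 = 4.17 times the stated requirement for men. 500/90 = 5.56 times for women. The ratio is 120/90 = 1.33. This shows that the protocol treats sex as relevant to vitamin K. It does not show that serum vitamin K, or any marker, differs by sex.

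Everything below is illustration. The assumed quantities are the sex difference d (in within-sex SDs), the share of women and the sample size. Tests are taken as two-sided at 0.05; the plan does not state sidedness.

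**(a) Induced pooled correlation, zero within each sex.** With share of women p and q = 1 − p,

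r = d1·d2·p·q / √[(1 + d1²·p·q)(1 + d2²·p·q)].

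With p = 0.5, p·q = 0.25. For d1 = 1.0 and d2 = 1.5: 0.375 / √(1.25 × 1.5625) = 0.375 / 1.398 = 0.27. The rejection rate uses Fisher's z.

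| d1, d2 | r | p < 0.05, total n = 40 | n = 60 | n = 100 |
|---|---|---|---|---|
| either is 0 | 0 | 5% | 5% | 5% |
| 0.5, 0.5 | 0.06 | 7% | 7% | 9% |
| 0.5, 1.0 | 0.11 | 10% | 13% | 19% |
| 1.0, 1.0 | 0.20 | 23% | 33% | 52% |
| 1.0, 1.5 | 0.27 | 39% | 55% | 77% |

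Under this model a correlation adjusted for sex is zero in every row.

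**(b) Contrast between weight groups, no true weight effect.** The spurious difference is d × (share of women in group 1 − share in group 2). For 20/30 vs 10/30 women and d = 1.5 it is 1.5 × 0.333 = 0.50 within-sex SD. The SD across men and women together, at half women, is √(1 + 0.25 × 1.5²) = 1.25, so this is 0.50/1.25 = 0.40 on that scale. False-positive rates were simulated with 30 per group and fixed sex counts.

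| Women per group | d = 0.5 | d = 1.0 | d = 1.5 |
|---|---|---|---|
| 18 vs 12 (60% vs 40%) | 0.10 SD, about 6% | 0.20 SD, about 8% | 0.30 SD, about 10% |
| 20 vs 10 (67% vs 33%) | 0.17 SD, about 9% | 0.33 SD, about 18% | 0.50 SD, about 30% |

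A linear model with weight group and sex held the rate at about 5% in all six cells.

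With d = 0, or with both groups drawn at random from populations with the same sex mix, the unadjusted test also stays at about 5%. With exactly equal counts of women it is conservative, at roughly 1% to 4.5% for d of 0.5 to 1.5.

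If sex is sampled at random within groups, with true shares of 60% and 40%, the unadjusted rates at 30 per group are somewhat higher than in the first row: 6.6%, 10.5% and 15.1%.

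**The case against.** **The main aim is untouched.** The second aim compares each person before and after, and sex does not change in six weeks. A reader might infer that sex mix could pass for an effect of the vitamin K diet itself. The documents do not support that, because a within-person change cannot be confounded by sex. This stands, and it limits the point to correlations and between-group contrasts. One qualification is that the only tests named are for independent groups, with no paired test. Also, leptin is listed in the final blood sample but not in the initial one. As listed, leptin can be compared only between people.

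**The weight-group contrast is inferred.** The plan does not say what the independent-samples t test compares, and the second aim could mean before-after within each weight group. This also stands, so the point applies to any such contrast that is made.

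**Enrolment of both sexes is inferred.** It is the natural reading of young adults with no stated restriction. A single-sex sample would remove the problem.

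**The requirement figures prove little.** A reader might take 4.17 vs 5.56 times requirement as evidence that serum levels differ by sex. Requirements are not serum levels, and the documents give no marker values by sex.

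**Chi square might be applied to sex by weight group.** It could be, since its variables are not named. That would describe an imbalance but not adjust for it.

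**Conclusion.** The point holds in a limited form. If both sexes enrol, the third aim's pooled correlations can be produced by sex alone, and any contrast between weight groups can be distorted when their sex mix differs. The analysis section contains nothing that would prevent or reveal the first of these.

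The size is unknown. Under the assumptions shown, the induced r runs from 0 to about 0.27, and false positives in a group contrast with 30 per group run from about 5% to about 30%. The lower ends apply if the markers do not differ by sex or, for group contrasts, if the sex mix is the same. The upper ends need sex differences of 1.0 to 1.5 SD and, for the contrast, 67% vs 33% women. None of these values comes from the documents.

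The documents do not support saying that the results will be biased, or that the before-after findings are at risk from sex. They do support prespecifying the adjustment, since it costs almost nothing and removes the ambiguity.

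**What to change.** - **Third aim.** Report partial correlations controlling for sex (on ranks where the variables are not normal), with men and women also shown separately as a check.
- **Any contrast between weight groups.** Replace the unadjusted test with a linear model containing weight group and sex, on the log scale where the outcome is skewed. Say in the plan which comparisons this covers.
- **Description.** State whether both sexes are eligible, and report the number of men and women in each weight group.

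The cost is a few lines in the SAP and one degree of freedom per model. Sex should be available from the clinical history already taken at the initial evaluation. Its contents are not listed, so confirm that sex is recorded. The intervention does not change. Adjusting for age or matching the groups on sex is optional and is not needed for this point.
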